### 6.1.3 End-of-Treatment Study Procedures

To be completed within 30 days of the last dose of study drug.

- Disease assessment including imaging (CT or MRI) of chest/abdomen/pelvis, and brain (if lesions found in screening), for tumor/lesion assessment
- Physical examination
- Vital signs
- Performance Status
- Evaluation of adverse events
- Concomitant medications
- Hematology labs (other than CBC with diff)
- Complete blood count (CBC) with differential and platelet count
- Blood chemistry assessment, including:
  - Alkaline phosphatase, ALT/AST, total bilirubin, calcium, phosphorus, BUN, creatinine, total protein, albumin, fasting glucose, potassium, sodium, chloride, bicarbonate,
  - Coagulation assessment, including PT/PTT/INR
- Urinalysis
- Electrocardiogram (ECG)
- Blood collection for ctDNA and cfDNA biomarkers
- Optional tumor biopsy for biomarker analysis and exploratory studies.

### 6.1.4 Post-treatment/Follow Up Visits

Patients will be followed every 3 months +/- 14 days for up to 18 months after enrollment or until disease progression.

The following procedures will be performed at the Follow Up Visit(s):

- Disease assessment including imaging (CT or MRI) of chest/abdomen/pelvis, and brain (if lesions found in screening) for tumor/lesion assessment. Scans would only be completed in follow-up for patients whose disease has not yet progressed since entering the study.
- Physical examination
- Vital signs
- Performance Status
- Evaluation of adverse events
- Concomitant medications
- Hematology labs (other than CBC w/ Diff)
- CBC with differential and platelet count
- Blood chemistry assessment, including:
  - Alkaline phosphatase, ALT/AST, total bilirubin, calcium, phosphorus, BUN, creatinine, total protein, albumin, fasting glucose, potassium, sodium, chloride, bicarbonate,
- Coagulation assessment, including PT/PTT/INR

- Urinalysis

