| 
Number of patients
    | 
A total of 27 patients will be enrolled into the study, with the goals of obtaining 24 evaluable patients. Using a Simon 2-stage design, if we do not observe at least 2 responses within the first 15 patients, enrollment will be stopped due to lack of efficacy.
  |
| 
Duration of Therapy
   | 
Patients may continue treatment until disease progression or up to 24 months from the time of study entry or until the study is closed.
   |
| 
Duration of Follow up
 | 
All patients will be followed for 12 months.
  |
| 
Duration of study
     | 
The study is estimated to reach completion 4 years from the time the study opens to accrual.
  |

|                             |  |
|-----------------------------|--|
| 
Study Drugs
          | 
Trametinib is a reversible and highly selective allosteric inhibitor of MEK1 and MEK2 activation and kinase activity. Trametinib will be administered as 2 mg orally once daily.
  |
| 
Safety Assessments
   | 
Safety assessments will be based on events occurring during the on-study period, defined as from the first dose of trametinib to 30 days after the last dose of trametinib or until resolution for serious adverse events. Safety will be assessed by reviewing adverse events (AEs), laboratory evaluations, physical examination, and imaging or procedures when clinically indicated. Toxicity will be graded according to the National Cancer Institute's Common Terminology Criteria for Adverse Events (version 4.03).
  |

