### 3.5 Duration of Follow Up

Patients will be followed for 30 days after completion of treatment or removal from study, or until death, whichever occurs first. Patients removed from study for unacceptable treatment related adverse event(s) will be followed until resolution or stabilization of all treatment related adverse events to Grade 2 or lower.

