### **6.1.5 Long Term/Survival Follow-up Procedures**

### **6.1.6 Discontinuation of Therapy**

The Investigator will withdraw a patient whenever continued participation is no longer in the patient's best interests. Reasons for withdrawing a patient include, but are not limited to, disease progression, the occurrence of an adverse event or a concurrent illness, a patient's request to end participation, a patient's non-compliance or simply significant uncertainty on the part of the Investigator that continued participation is prudent. There may also be administrative reasons to terminate participation, such as concern about a patient's compliance with the prescribed treatment regimen.

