| Laboratory proceduresg |                        |                  |           |           |            |            |                           |           |           |            |            |                        |                  |            |
| CBC w/ Diff                              | X                      | X                |           |           |            |            | X                         |           |           |            |            | X                      | X                |            |
| Blood chemistry                          | X                      | X                |           |           |            |            | X                         |           |           |            |            | X                      | X                |            |

| Period/Procedure                     | Screening a | Cycle 1   |           |            |            |            | Cycle 2 and future Cycles |           |            |            |            | End of Treatment visit            | Follow-up visits            |
|--------------------------------------|------------------------|-----------|-----------|------------|------------|------------|---------------------------|-----------|------------|------------|------------|-----------------------------------|-----------------------------|
| Study Day/Visit Day                  | -28 to 0 (+/- 3)       | 1 (+/- 3) | 8 (+/- 3) | 15 (+/- 3) | 22 (+/- 3) | 29 (+/- 3) | 1 (+/- 3)                 | 8 (+/- 3) | 15 (+/- 3) | 22 (+/- 3) | 29 (+/- 3) | 30d after last dose of study drug | FU every 3 months (+/- 14d) |
| Coagulation                          | X                      | X         |           |            |            |            | X                         |           |            |            |            | X                                 | X                           |
| Urinalysis                           | X                      | X         |           |            |            |            | X                         |           |            |            |            | X                                 |                             |
| Pregnancy test (HCG)                 | X                      | X         |           |            |            |            | X                         |           |            |            |            |                                   |                             |

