- f. Disease assessment documentation at screening (presence of measurable disease) and on trial includes restaging (per RECIST), which will occur q2 cycles beginning cycle #3. During Follow-up visits, scans would only be completed in follow-up for patients whose disease has not yet progressed since entering the study
- g. **Blood chemistry labs:** alkaline phosphatase, ALT/AST, total bilirubin, calcium, phosphorus, (BUN), creatinine, total protein, albumin, fasting glucose, potassium, sodium, chloride, bicarbonate

**Coagulation labs:** PT/PTT/INR

Serum or urine pregnancy test must be negative within 3 days prior to start of C1D1.

h. **Imaging exams:** if known lesions, brain imaging every other cycle starting with cycle #3.

**Cardiac assessments** to be completed every 3 months after cycle #2.

**Ophthalmology exams** to be completed prior to cycle 2 day 1, again at 6 months, and then annually thereafter unless clinically indicated sooner.

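### Collection of survival status after disease progression is not assured, so the 1-year Kaplan-Meier overall survival endpoint could be censored informatively

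*Combined protocol and SAP*

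**What the plan says.** OS is defined in 2.4.2 and 8.3.3(d) as time from first dose to death from any cause over 1 year, summarised by a Kaplan-Meier median with a 95% confidence interval. Section 8.3.1 includes every patient who receives a dose in the efficacy analysis. Follow-up is described in several places.

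- Abstract, Duration of Follow up: "All patients will be followed for 12 months". No start date is given.
- Section 3.5: "Patients will be followed for 30 days after completion of treatment or removal from study, or until death, whichever occurs first". The Abstract uses a similar window for safety, "defined as from the first dose of trametinib to 30 days after the last dose of trametinib".
- Section 6.1.4, lead sentence: "Patients will be followed every 3 months +/- 14 days for up to 18 months after enrollment or until disease progression".
- Section 6.1.4, imaging item: "Scans would only be completed in follow-up for patients whose disease has not yet progressed since entering the study". Table 6.1, note f, repeats this.
- Table 6.1, follow-up column: "FU every 3 months (+/- 14d", with no stop at progression and no row for survival status.
- Section 6.1.5: the heading "Long Term/Survival Follow-up Procedures" is followed directly by 6.1.6, with no text and no redaction mark.

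On deaths, section 7.7 requires every serious adverse event (SAE) up to at least 30 days after treatment stops to be reported to the drug supplier, and after that only those suspected to be drug-related. Appendix 4, section 3.2, lists death as an SAE. It has all SAEs entered in the trial database and reported to the coordinating center once a site is aware of them, with no time or relatedness limit in that text.

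**The concern.** To estimate OS to 1 year, each dosed patient's vital status must be known to month 12 or to a censoring date unrelated to prognosis. Treatment normally ends at progression (section 3.4). A site that follows 3.5, or the lead sentence of 6.1.4, literally would lose contact at or soon after progression. Progression often changes the risk of death, so that censoring would be informative, and the Kaplan-Meier curve would describe mainly patients who had not progressed or had only just done so. In a multicenter trial, sites could also apply different rules, which would mix two kinds of censoring in 27 patients. What is at stake is a secondary, estimation-only endpoint. No test or stopping rule uses it.

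**Working it through.** **Step 1. The texts side by side.** The question is whether each one covers a progressed patient to 12 months from first dose.

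| Place | Length | Counted from | Covers OS after progression? |
|---|---|---|---|
| Abstract, Duration of Follow up | 12 months, all patients | not stated | Yes, if counted from first dose or later |
| Section 3.5 | 30 days | end of treatment or removal | No |
| Section 6.1.4, lead sentence | up to 18 months, or progression | enrollment | No |
| Section 6.1.4 imaging item; Table 6.1 note f | imply visits by progressed patients | not stated | Yes, if those visits continue to month 12 |

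No passage says which rule governs. The sharpest conflict is between the Abstract and the lead sentence of 6.1.4, and 6.1.4 also conflicts with its own imaging item. Section 6.1.5, where this would be settled, is empty. The 1-year limit in the OS definition implies administrative censoring at 1 year, but no rule covers censoring before that. Patients who stop treatment without progression are covered by the 3-monthly visits until they progress, so the gap concerns progressed patients.

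**Step 2. Size if follow-up ends 30 days after treatment stops for progression.** The plan gives no progression-free survival (PFS) or OS rates, so there is no figure of its own to reproduce and every rate below is an assumption. Time is in months.

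- PFS hazard l = ln 2 / median PFS, with the median 3, 3.5 or 4.
- Share d of PFS events that are deaths: 10, 15 or 20%.
- Post-progression death hazard m = ln 2 / median post-progression survival, with the median 4, 6 or 9.
- S0(t) = exp(-l t) is the probability of being alive and progression-free.
- P1(t) is the probability of being alive and having progressed within the last w months.
- Recorded death hazard = [d l S0(t) + m P1(t)] / [S0(t) + P1(t)]. The Kaplan-Meier limit at 12 months is exp(-integral of this hazard from 0 to 12).
- w = 30/30.44 if the last dose is at progression. It is 58/30.44 or 86/30.44 if the last dose is 28 or 56 days later.

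Worked case, medians 3 and 6, d = 10%: l = 0.231 and m = 0.1155. True 12-month OS = S0(12) + [(1-d) l / (l-m)] × [exp(-12m) - exp(-12l)] = 0.0625 + 1.8 × (0.25 - 0.0625) = 0.400. The recorded curve gives 0.627. With d = 20%, true OS is 0.0625 + 1.6 × 0.1875 = 0.3625, and the recorded curve gives 0.505. Among 27 patients, about 5 of 16 first-year deaths (d = 10%) or 7 of 17 (d = 20%) would be recorded.

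Across the grid of 3 × 3 × 3 = 27 scenarios, the true median OS lies within 12 months in 21 (7.2 to 11.7 months).

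| Last dose | 12-month OS too high by | First-year deaths captured | Median OS reads as not reached |
|---|---|---|---|
| At progression | 7.8 to 28.0 points | 31 to 47% | 20 of 21 |
| 28 days later | 5.6 to 18.7 points | 43 to 55% | 14 of 21 |
| 56 days later | 4.0 to 12.7 points | 52 to 65% | 9 of 21 |

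The later rows matter because 2.4.2 and 8.3.3 foresee treatment beyond progression.

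**Step 3. Where the bias vanishes or reverses.** The sign depends on d l (death hazard before progression) against m (after). These cases have the last dose at progression.

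- Medians 3 and 6, d = 50%: d l = 0.5 × 0.231 = 0.1155 = m, and the bias is 0.
- Medians 3 and 9, d = 30%: d l = 0.069, m = 0.077, bias +1.6 points.
- Medians 3 and 12, d = 30%: d l = 0.069, m = 0.058, bias -2.7 points.
- Medians 2 and 9, d = 30%: d l = 0.104, m = 0.077, bias -5.2 points.

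This bias is also 0 if the Abstract's 12 months are applied from first dose, or if visits continue after progression to month 12.

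**The case against.** The best defence is that the intent is clear. The Abstract follows all patients for 12 months, which matches the OS window, and sections 3.6.1 and 3.6.2 place study completion 12 months after primary completion. The 30 days in 3.5 match the safety window, and the next sentence there concerns resolution of adverse events, so 3.5 reads naturally as safety follow-up. Section 6.1.6 lists progression as a reason to withdraw a patient, but it is about stopping therapy and does not say that survival follow-up ends. All of this stands, and it narrows the point. It does not supply a procedure, a start date or an order of precedence, and the lead sentence of 6.1.4 still ends visits at progression.

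A reader might infer that nobody's survival is tracked beyond 30 days after treatment. The documents do not support that, because patients who stop without progression have 3-monthly visits. A reader might also infer that later deaths can be found only if a site keeps up visits or applies the Abstract's rule. That is not established either. The 30-day and relatedness limits in 7.7 govern reporting to the drug supplier, whereas Appendix 4, section 3.2, has no such limit, although the Abstract's on-study safety window may restrict it. SAE reporting may therefore capture deaths that a site hears of. It schedules no check, and it does not show that the other patients are alive.

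**Conclusion.** The point holds for patients who have progressed: 1-year OS is not assured. It would go too far to say that it cannot be estimated. Confidence in the textual gap is high and does not rest on the model. Confidence in the size and direction of any bias is low. The range of about 8 to 28 points too high needs the assumed rates in the grid, the last dose at progression, follow-up ending 30 days later, and no later deaths picked up by other routes. A reader might take it as the expected error in this trial. The documents give no rates to support that, and other plausible inputs give zero or negative bias. The primary response-rate analysis and the stage-1 rule are not touched. It should be fixed, because survival contacts that are missed may not be recoverable later.

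**What to change.** - Complete 6.1.5 and add a row to Table 6.1: a survival-status check by telephone or records, about every 3 months, for every dosed patient until death or at least 12 months after first dose. It should apply regardless of progression or treatment discontinuation, unless consent is withdrawn.
- Reconcile the Abstract, 3.5 and 6.1.4 with one stated start date. Label the 30 days in 3.5 as safety follow-up if that is what is meant, and limit the progression stop in 6.1.4 to scans.
- State that ending treatment under 6.1.6 does not end survival follow-up.
- State that OS is censored at the date last known alive, at most 1 year from first dose.

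The cost is small: about 4 checks × 27 patients = at most about 108 remote contacts, one table row, some wording, and consent that allows contact after progression. No extra scans or clinic visits are needed.

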### **6.1.5 Long Term/Survival Follow-up Procedures**

### **6.1.6 Discontinuation of Therapy**

The Investigator will withdraw a patient whenever continued participation is no longer in the patient's best interests. Reasons for withdrawing a patient include, but are not limited to, disease progression, the occurrence of an adverse event or a concurrent illness, a patient's request to end participation, a patient's non-compliance or simply significant uncertainty on the part of the Investigator that continued participation is prudent. There may also be administrative reasons to terminate participation, such as concern about a patient's compliance with the prescribed treatment regimen.

**Table 6.1 Schedule of Study Procedures and Assessments**

| Period/Procedure                         | Screening a | Cycle 1          |           |           |            |            | Cycle 2 and future Cycles |           |           |            |            | End of Treatment visit | Follow-up visits |            |
|--|------------------------|------------------|-----------|-----------|------------|------------|---------------------------|-----------|-----------|------------|------------|------------------------|------------------|------------|
|  |                        | -28 to 0 (+/- 3) | 1 (+/- 3) | 8 (+/- 3) | 15 (+/- 3) | 22 (+/- 3) | 29 (+/- 3)                | 1 (+/- 3) | 8 (+/- 3) | 15 (+/- 3) | 22 (+/- 3) |                        |                  | 29 (+/- 3) |
| Informed consent                         | X                      |                  |           |           |            |            |                           |           |           |            |            |                        |                  |            |
| Baseline conditions b         | X                      |                  |           |           |            |            |                           |           |           |            |            |                        |                  |            |
| AE assessment                            |                        | X                | X         | X         |            |            | X                         |           |           |            |            | X                      | X                |            |
| Concomitant medications                  | X                      | X                | X         | X         |            |            | X                         |           |           |            |            | X                      | X                |            |
| Blood collection for biomarkers          | X                      | X                | X         | X         |            |            | X                         |           |           |            |            | X                      |                  |            |
| Required Research Biopsy c    | X                      |                  |           |           |            |            |                           |           |           |            |            |                        |                  |            |
| Optional Research Biopsy                 |                        |                  |           |           |            |            | X +/- 7d (C2only)         |           |           |            |            | X                      |                  |            |
| Treatment/Drug Administration     |                        |                  |           |           |            |            |                           |           |           |            |            |                        |                  |            |
| Trametinib d                  |                        | X                | X         | X         |            |            | X                         |           |           |            |            |                        |                  |            |
| Clinical procedures               |                        |                  |           |           |            |            |                           |           |           |            |            |                        |                  |            |
| Physical exam                            | X                      | X                |           |           |            |            | X                         |           |           |            |            | X                      | X                |            |
| Vital signs                              | X                      | X                |           |           |            |            | X                         |           |           |            |            | X                      | X                |            |
| Medical history e             | X                      |                  |           |           |            |            | X                         |           |           |            |            | X                      | X                |            |
| Disease assessment f          | X                      |                  |           |           |            |            | X                         |           |           |            |            | X                      | X                |            |
| Performance status                       | X                      | X                |           |           |            |            | X                         |           |           |            |            | X                      | X                |            |
| Laboratory proceduresg |                        |                  |           |           |            |            |                           |           |           |            |            |                        |                  |            |
| CBC w/ Diff                              | X                      | X                |           |           |            |            | X                         |           |           |            |            | X                      | X                |            |
| Blood chemistry                          | X                      | X                |           |           |            |            | X                         |           |           |            |            | X                      | X                |            |

| Period/Procedure                     | Screening a | Cycle 1   |           |            |            |            | Cycle 2 and future Cycles |           |            |            |            | End of Treatment visit            | Follow-up visits            |
|--------------------------------------|------------------------|-----------|-----------|------------|------------|------------|---------------------------|-----------|------------|------------|------------|-----------------------------------|-----------------------------|
| Study Day/Visit Day                  | -28 to 0 (+/- 3)       | 1 (+/- 3) | 8 (+/- 3) | 15 (+/- 3) | 22 (+/- 3) | 29 (+/- 3) | 1 (+/- 3)                 | 8 (+/- 3) | 15 (+/- 3) | 22 (+/- 3) | 29 (+/- 3) | 30d after last dose of study drug | FU every 3 months (+/- 14d) |
| Coagulation                          | X                      | X         |           |            |            |            | X                         |           |            |            |            | X                                 | X                           |
| Urinalysis                           | X                      | X         |           |            |            |            | X                         |           |            |            |            | X                                 |                             |
| Pregnancy test (HCG)                 | X                      | X         |           |            |            |            | X                         |           |            |            |            |                                   |                             |
| Imaging procedureh |                        |           |           |            |            |            |                           |           |            |            |            |                                   |                             |
| Imaging (CT or MRI) h     | X                      |           |           |            |            |            | X                         |           |            |            |            | X                                 | X                           |
| Cardiac Assessment (ECHO, MUGA)      | X                      |           |           |            |            |            | X                         |           |            |            |            |                                   |                             |
| ECG/EKG (in triplicate)              | X                      | X         |           |            |            |            | X                         |           |            |            |            | X                                 |                             |
| Ophthalmology Exam                   | X                      |           |           |            |            | X          |                           |           |            |            |            |                                   |                             |

- a. Screening procedures and assessments must be completed -28d of Day 1 visit. Screening labs completed within 3 days of C1D1 need not be repeated.
- b. Baseline conditions include all ongoing medical conditions at time of consent.
- c. **Archival tissue collection** and research biopsy during screening and for exploratory biomarker assessments. Biopsy will be CT guided (or via bronchoscopy if unable to obtain) unless deemed medically unsafe.  
**Optional tumor biopsy:** for exploratory analyses, best response and resistance (C2D1 +/- 7d and at end of treatment visit).
- d. Trametinib will be taken with a full glass of water, without food, at least 1 hour before or 2 hours after a meal, 2mg, once a day. See section 5.0 Table 5.1 for treatment regimen details. Safety assessments (AE assessments and concomitant medication check) to be completed during clinic visits.
- e. Medical history documentation of past conditions or procedures that have been resolved.
- f. Disease assessment documentation at screening (presence of measurable disease) and on trial includes restaging (per RECIST), which will occur q2 cycles beginning cycle #3. During Follow-up visits, scans would only be completed in follow-up for patients whose disease has not yet progressed since entering the study
- g. **Blood chemistry labs:** alkaline phosphatase, ALT/AST, total bilirubin, calcium, phosphorus, (BUN), creatinine, total protein, albumin, fasting glucose, potassium, sodium, chloride, bicarbonate

**Coagulation labs:** PT/PTT/INR

Serum or urine pregnancy test must be negative within 3 days prior to start of C1D1.

h. **Imaging exams:** if known lesions, brain imaging every other cycle starting with cycle #3.

**Cardiac assessments** to be completed every 3 months after cycle #2.

**Ophthalmology exams** to be completed prior to cycle 2 day 1, again at 6 months, and then annually thereafter unless clinically indicated sooner.

